3.11 Follow-up of Subjects Withdrawn from Study

Subjects who receive any amount of IP and discontinue early from the study will be requested to return for the Early Discontinuation Visit procedures (see Section 3.8.2.6) as soon as practical following decision to withdraw (at least within 14 days after the termination date) if the subject is willing. If discontinuation is due to a TEAE (or other reason) during the treatment period (which includes IP Run-in maintenance and CS Tapering/IP Maintenance phases) assessments specified for the two additional visits in the

Safety/Follow-up phase should be performed, i.e., Week 42 (Visit 15) and Week 45 (Visit 16) corresponding to time points 6 and 9 weeks after the last IP administration.

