### 7.3. MISSING DATA

Imputation for missing values will be applied to continuous efficacy endpoints using the LOCF or the WOCF method.

Primary efficacy endpoint of CS dose:

For the primary efficacy endpoint of CS dose, the WOCF method will be applied to subjects who discontinued early from the study with adverse outcomes related to MG, defined as those subjects who met ALL criteria below:

- The primary reason for discontinuation is one of the following: “Adverse Event”, “Death”, “Discontinuation due to MG crisis requiring hospitalization”, or “MG worsening (CS-unresponsive or 2nd episode)”
- The subject had at least one adverse event (AE) with preferred term (PT) of either “Myasthenia gravis crisis” or “Myasthenia gravis”
- The AE is serious, with the reason for seriousness being “Required/Prolonged Hospitalization” or “Resulted in Death”
- The onset date/time of the AE is on or after the start date/time of the first infusion of study medication, i.e., the AE is treatment-emergent

For these subjects, the worst values, i.e., the highest average daily CS dose available among all eligible visits [including the Baseline visit, all post-baseline scheduled visits, and the Early Termination visit(s)], will be carried forward to impute the missing CS dose for all remaining visits.

For subjects who discontinued the study early due to any other reasons, the LOCF method will be used to impute the missing values, i.e., the last non-missing post-baseline CS dose value available among all eligible visits [including all post-baseline scheduled visits and the Early Termination visit(s)] will be carried forward to impute missing values for all remaining visits.

Note for the primary efficacy endpoint of CS dose, the values to be considered as candidates for carrying forward are the derived average daily CS dose at the relevant scheduled visits, incorporating potential changes in the prescribed CS dose within the prior 3 weeks (see section 16.1.1 for derivation details).

Other continuous efficacy variables:

For all other continuous efficacy variables and for all subjects who discontinued the study early, regardless of the reason, the LOCF method will be used to impute the missing values, i.e., the last non-missing post-baseline value (including scheduled, unscheduled, and early termination) will be carried forward to impute missing values for all remaining visits.

All continuous efficacy variables:

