## 16. EFFICACY OUTCOMES

### 16.1. PRIMARY EFFICACY

#### 16.1.1. PRIMARY EFFICACY VARIABLE & DERIVATION

The primary efficacy variable is the percent of subjects achieving a 50% or greater reduction in CS dose (prednisone or equivalent) at Week 39 (Visit 14) from Baseline/Week 0 (Visit 1).

The prescribed CS dose (mg) is reported under item 3 on the CS Use page of the eCRF. Prednisone equivalent dose is also collected on the eCRF if prednisone is not the prescribed CS. The prednisone dose (if prednisone is the prescribed CS) or prednisone-equivalent dose (if prednisone is not the prescribed CS) will be used for primary analysis. The frequency of prescribed dose (Item 4) is reported as either "total daily" or "every other day". For analyses "every other day" doses will be normalized to daily doses as described in the protocol ( $[\text{every other day dose}]/2 = \text{daily dose}$ ). All CS use data will be presented in a listing.

At each scheduled visit, a subject was to enter all prescribed CS doses that were in effect since the date of the last scheduled visit up to the date of the current scheduled visit on the CS Use page of the eCRF, including all changes to the prescribed CS doses that occurred during this time period. In some instances an unscheduled visit could have been used to document changes to the prescribed CS doses.

The average daily CS dose will be derived for each subject at each scheduled visit as follows based on the prescribed dose and the time interval taking into account any prescribed dose changes between routinely scheduled visits entered as either Unscheduled Visits or as Add Entry fields under the routinely scheduled visits:

- For each scheduled visit, define the time period for deriving the average daily CS dose at the current scheduled visit as follows: from the date of the last scheduled visit + 1 to the date of the current scheduled visit, inclusive. For example, for Week 39, the time period would be from the day after the date of visit for Week 36 to the date of visit for Week 39, inclusive. For the purpose of deriving the primary efficacy variable, Baseline and ET visits are also considered scheduled visits. Note a subject may have one or two Early Termination visits. The time periods for these visits are defined as follows:
  - Baseline Visit: from the day after the date of visit for Week -3 to the date of visit for Week 0, inclusive.

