  - Early Termination Visit 1: from the day after the date of the last scheduled visit to the date of visit for the Early Termination Visit 1, inclusive.
  - Early Termination Visit 2 (if performed): from the day after the date of the Early Termination Visit 1 to the date of visit for the Early Termination Visit 2, inclusive.

Document: CCI

Author: PPD

Version Number:

Version Date:

Final 2.0  
12Apr2019

Template No: CCI

Effective Date: 01Apr2016

Reference: CCI

Copyright © 2009, 2010, 2012, 2016 CCI. All rights reserved.

The contents of this document are confidential and proprietary to CCI. Unauthorized use, disclosure or reproduction is strictly prohibited.

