## Analysis Plan

- Calculate the total CS dose for each distinctive CS dose regimen in effect during this time period:
  - If the frequency is “total daily” for the CS dose regimen, then total CS dose = daily CS dose x number of days this CS dose regimen in effect
  - If the frequency is “every other day” for the CS dose regimen, then total CS dose = (every other day CS dose / 2) x number of days this CS dose regimen in effect
- Calculate the total CS dose for the time period as the sum of the total CS doses for all distinctive CS dose regimens in effect during this time period.
- Calculate the average daily CS dose: Average daily CS dose = Total CS dose / (date of current scheduled visit – date of last scheduled visit)

The calculated average daily CS dose at the scheduled visits will be used in all relevant efficacy analyses.

Note, as stated above, in general the average daily CS dose will only be derived at the scheduled visits, which include early termination visit(s). Unscheduled visits, if any, typically will fall between two scheduled visits and hence any prescribed CS dose data at unscheduled visits will automatically be taken into consideration in the algorithm above.

The only exception to this rule will be when a subject has an unscheduled visit AFTER the last scheduled visit and prescribed CS dose data were captured at this last unscheduled visit. For example, there may be rare occasions when a subject withdrew early from the study but did not return for any early termination visits; however, it was known that the subject’s prescribed CS dose increased after the last scheduled visit and such dose increases were captured using an unscheduled visit. In this case the average daily CS dose will be additionally derived at the last unscheduled visit, and the time period for this visit will be: from the day after the last scheduled visit to the date of visit for the last unscheduled visit, inclusive.

The derived average daily CS dose at an unscheduled visit after the last scheduled visit will not be used directly in any summary tables that use scheduled visits but will be eligible for the LOCF/WOCF algorithm. This approach is deemed to be conservative should such an unscheduled visit capture an increase in CS dose.

Missing either the prescribed dose or the frequency of the dose for at least 1 CS dosing record at a visit will lead to missing derived average daily dose.

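### When a discontinued subject's last steroid record is the visit at which the dose was raised, LOCF carries forward the lower dose from before the increase and can score the subject a Week 39 responder

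*SAP*

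**What the plan says.** **What is carried forward.** SAP 7.3 states that the candidate values for the steroid endpoint are "the derived average daily CS dose at the relevant scheduled visits, incorporating potential changes in the prescribed CS dose within the prior 3 weeks". The candidate is therefore an average, not the dose ordered at the visit. SAP 16.1.2 describes the same step more loosely, as imputing the prescribed dose at Week 39.

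**The averaging interval.** SAP 16.1.1 defines it for scheduled visits as "from the date of the last scheduled visit + 1 to the date of the current scheduled visit, inclusive". For the first early termination (ET) visit it is "from the day after the date of the last scheduled visit to the date of visit for the Early Termination Visit 1, inclusive". For an unscheduled visit after the last scheduled one it is "from the day after the last scheduled visit to the date of visit for the last unscheduled visit, inclusive". All three look backward and stop on the visit's own date.

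**Who receives LOCF.** SAP 7.3: "For subjects who discontinued the study early due to any other reasons, the LOCF method will be used to impute the missing values". The alternative, WOCF, needs among other things a serious myasthenia gravis (MG) adverse event with hospitalization or death.

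**Later records.** Protocol 3.11 requests an Early Discontinuation Visit "if the subject is willing" and says two further follow-up visits should be performed. SAP 6.4 makes early termination data eligible for LOCF. SAP 16.1.1 also makes the late unscheduled average eligible and adds: "This approach is deemed to be conservative should such an unscheduled visit capture an increase in CS dose".

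**When increases are ordered.** Protocol 3.3.3 triggers an increase on a QMG rise of at least 4 points during the tapering phase. QMG is scored at every scheduled visit, and Protocol 3.8.2 requires the dose prescribed at each visit to be recorded.

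**The concern.** A dose ordered at a visit takes effect at the end of that visit's averaging interval or after it. It reaches the derived average only through the next record. For a subject who has no next record, LOCF uses the dose that preceded the increase.

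Such a subject has met the worsening definition and may have a final prescription well above half of baseline, yet can enter the primary analysis as a steroid-sparing success. The same carried-forward value feeds the secondary endpoint, percent reduction in daily dose (SAP 16.2.2.1). The observed-case analysis in SAP 16.1.4 does not expose the problem, because it drops these subjects instead of counting them as failures.

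In a trial of 60, each misclassified subject moves an arm's response rate by 1/30 = 3.3 points.

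**Working it through.** **1. The plan's own figure.** Protocol 5.2 gives 24 per group for 70% versus 30%, two-sided alpha 0.05 and 80% power. With pooled variance and no continuity correction:

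n = [1.960 × √(2 × 0.5 × 0.5) + 0.842 × √(0.7 × 0.3 + 0.3 × 0.7)]² / 0.4² = (1.386 + 0.545)² / 0.16 = 23.3, rounded up to 24.

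Allowing for 20% discontinuation, 48 / 0.8 = 60, or 30 per arm. The figure reproduces. It does not decide the point, but it supplies the arm size used in step 5.

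**2. Weight of an increase ordered at the last visit.** Let d be the dose before the visit, r the dose ordered at it, and 21 days the interval. By SAP 16.1.1 the average is total dose divided by days:

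- new dose starts the next day: A = 21d / 21 = d (weight 0);
- new dose starts on the visit day: A = (20d + r) / 21 (weight 1/21).

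**3. Worked cases.** The taper step is 10 mg above 40 mg and 5 mg otherwise (Table 3-1). The increase is 20 mg at 15 mg or more and 15 mg below that (Table 3-3). There is no later record.

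| Baseline (mg) | Week of increase | d → r (mg) | Reduction, A = d | Reduction, visit day counted | Reduction on ordered dose |
|---|---|---|---|---|---|
| 20 | 18 | 5 → 20 | 75% | 71.4% | 0% |
| 30 | 21 | 10 → 25 | 66.7% | 64.3% | 16.7% |
| 40 | 27 | 10 → 25 | 75% | 73.2% | 37.5% |
| 60 | 30 | 15 → 35 | 75% | 73.4% | 41.7% |

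All four are responders under LOCF and non-responders on the ordered dose. Counting the visit day changes the result only at the boundary. For baseline 20 mg, on 10 mg and raised to 25 mg, the average is (200 + 25)/21 = 10.7 mg. The reduction is then 46.4% instead of 50%.

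The unscheduled-visit rule has the same gap. Take baseline 20 mg, on 0 mg, seen 10 days after the last scheduled visit, with 15 mg ordered that day. The average is (9 × 0 + 15)/10 = 1.5 mg, a 92.5% reduction.

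By contrast, if the subject in the first row attends an ET visit after the increase, that visit averages 20 mg. The reduction is 0%, correctly a non-responder.

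**4. Enumeration.** Baselines 15 to 60 mg in 5 mg steps (10 values), uninterrupted taper, and a first increase at each visit from Week 12 to Week 36 (9 visits) give 90 paths. A path is misclassified when the carried-forward value is at or below half of baseline and the ordered dose is above it.

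| Taper stops at | Misclassified, A = d | Misclassified, visit day counted |
|---|---|---|
| 5 mg | 52 of 90 | 47 of 90 |
| 0 mg | 45 of 90 | 40 of 90 |

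**5. Effect on power (the number of cases is an assumption).** Exact power of the unstratified, uncorrected chi-square test, 30 per arm, with m false responders added:

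| m | Placebo only: rates | Power | m in both arms: rates | Power |
|---|---|---|---|---|
| 0 | 70% vs 30% | 89.6% | 70% vs 30% | 89.6% |
| 1 | 70% vs 33.3% | 83.5% | 73.3% vs 33.3% | 89.7% |
| 2 | 70% vs 36.7% | 75.6% | 76.7% vs 36.7% | 89.9% |
| 3 | 70% vs 40% | 66.3% | 80% vs 40% | 90.5% |

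The planned test is the stratified CMH, or an exact test when cells are sparse, so these figures show scale only.

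**The case against.** **The pattern is off the protocol's main path.** A reader might infer that, because increases are ordered at scheduled visits, the last attended visit is usually one of them. The documents do not support that. Protocol 3.1 has the raised dose assessed over the next two visits, and withdrawal follows failure to improve by the second of them or the need for a second increase. A subject whose worsening does not respond normally has later averages that contain the raised dose. An attended ET, follow-up or later unscheduled visit also captures it. This stands, and it limits the point to subjects with no later record. It does not remove it, because attendance after withdrawal depends on the subject.

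A second episode is one route within the protocol. Baseline 25 mg, raised from 5 to 20 mg at Week 21, stable at Weeks 24 and 27, re-tapered to 10 mg, worsening again at Week 33. Withdrawal is then required. Without hospitalization or a later record, LOCF carries 10 mg, a 60% reduction.

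**The enumeration is not a rate.** A reader might take 52 of 90 as a risk of about 58%. It is an equal-weight count, conditional on the exit pattern, with none of the 10 paths at Week 12 affected and all 30 at Weeks 21 to 27. This stands.

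**The direction is toward the null if cases fall in placebo.** That means lost power in a proof-of-concept study, not a false-positive risk. This stands for that assumption; the documents give no split by arm.

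**The visit list in SAP 7.3.** Its LOCF list names only scheduled and early termination visits, so a reader might infer that a late unscheduled visit is excluded. SAP 6.4, 16.1.1 and 16.1.2 all make it eligible. This is a wording mismatch only.

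**A corrected rule would treat discontinuers differently from completers,** for whom a dose ordered after the Week 39 assessments does not count. This stands, and it is why the fix excludes the ET visit and keeps the unmodified analysis alongside.

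**Conclusion.** The rule gives a wrong classification in a defined group: LOCF subjects whose final steroid record is the visit at which an increase was ordered. The early termination visit, the unscheduled-visit provision, WOCF and the observed-case analysis do not correct it for them.

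The size is unknown. The enumeration shows that misclassification is common within the pattern, not that the pattern is common. The power loss assumes one to three cases, all in placebo. If the cases are spread equally, the cost is inflated response rates in both arms. The lag also withholds credit for a taper step ordered at the last visit, but those steps are 5 to 10 mg against increases of 15 to 20 mg.

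This should be fixed, but it does not by itself undermine the trial. It is separate from another mismatch: Protocol 5.1.3.1 makes every withdrawal for MG worsening a non-responder, whereas the SAP's WOCF criteria require a serious event. Restoring the protocol rule would remove the cases recorded as MG worsening. It would not remove subjects whose dose was raised and who then left for another recorded reason, such as withdrawn consent.

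**What to change.** In SAP 7.3 and 16.1.1, add a rule for a discontinued subject under LOCF who has no steroid record after the last attended on-study visit, the ET visit not being counted as one. If the dose prescribed at that visit exceeds the derived average, carry forward the prescribed dose. Report the unmodified LOCF result as a sensitivity analysis. As a wording correction, align the eligible-visit list in 7.3 with 16.1.1 and 16.1.2. No clinical rule changes.

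The cost is about two sentences, one programming step and one extra table. The protocol already requires the prescribed dose to be recorded at each visit. Because SAP 16.1.1 describes the steroid page as holding doses in effect up to the visit date, confirm before unblinding that it also holds the newly ordered dose.

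The downside is small: the rule is one-sided, since a final untested taper step is still not credited, and it differs from how completers are scored at Week 39.

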#### 6.4. RETESTS, UNSCHEDULED VISITS AND EARLY TERMINATION DATA

In general, for by-visit summaries, data recorded at the nominal visit will be presented. Unscheduled measurements will not be included in by-visit summaries, but will contribute to the baseline, last observation carried forward (LOCF; defined in Section 7.3) and the best/worst case value where required. Unscheduled visits will also contribute to the analyses of all CS dosage variables (See Section 16.1.1 for derivation details).

In the case of a retest (same visit number assigned), the latest available measurement for that visit will be used for by-visit summaries.

Early termination (discontinuation) visit data will not be mapped to the next available visit number for by-visit summaries; instead, they will be summarized under a separate "Early Termination 1" visit. By-visit summaries will only present those visits where an assessment is scheduled to be collected. Early termination data will be eligible for the LOCF/worst observation carried forward (WOCF; defined in Section 7.3) endpoint but will not be mapped for observed case (OC; defined in Section 7.3) analysis.

Subjects who discontinued during the treatment phase will be those who did not complete the study, i.e. "No" for Item 1 reported on the End of Study page of the eCRF, and did not reach the scheduled Week 39 visit. These subjects should return for two additional visits in the follow-up phase, i.e., Week 42 (Visit 15) and Week 45 (Visit 16) corresponding to time points 6 and 9 weeks after the last IP administration. If an early discontinued subject returned for two follow-up visits, they will be summarized under separate "Early Termination 1" visit and "Early Termination 2" visit, respectively.

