**16.1.2. MISSING DATA METHODS FOR PRIMARY EFFICACY VARIABLE**

Subjects who discontinued the study early with adverse outcomes related to MG will be considered as not achieving a 50% or greater reduction. The missing dose reduction at Week 39 will be imputed using the WOCF method.

For subjects who do not have CS dose prescribed at Week 39 due to other reasons, the LOCF will be used to impute the prescribed CS dose at Week 39. The last non-missing post-baseline value (including scheduled, unscheduled, and early termination) prior to Week 39 will be carried forward to determine whether a subject achieves a 50% or greater reduction at Week 39. Subjects with no post-baseline CS dose will be excluded from analysis.

Refer to section 16.1.4 for analyses on sensitivity to missing data.

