### 16.2.2. MISSING DATA METHODS FOR SECONDARY EFFICACY VARIABLE(S)

#### 16.2.2.1. Missing Data Method for Percent Reduction in Daily CS Dose at Week 39

For subjects who discontinued the study early with adverse outcomes related to MG, the missing percent reduction in CS dose at Week 39 will be imputed using the WOCF method. For subjects who have missing CS dose reduction at Week 39 due to other reasons, the missing CS dose will be imputed using the LOCF approach for continuous endpoints as detailed in Section 7.3.

Missing data will also be handled with the OC approach, where the analysis will be based on observed non-missing data only and subjects with missing data at Week 39 will be excluded from the analysis.

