## 16.3. EXPLORATORY EFFICACY

### 16.3.1. EXPLORATORY EFFICACY VARIABLES & DERIVATIONS

#### 16.3.1.1. Percent of Subjects Achieving a 75% or Greater Reduction in CS Dose (Prednisone or Equivalent) at Week 39 from Baseline

This endpoint will be derived in the same way as the primary endpoint described in Section 16.1.1.

#### 16.3.1.2. Percent of Subjects CS-free at Week 39

Subjects whose daily CS dose prescribed at Week 39 is 0 mg will be considered CS-free.

#### 16.3.1.3. Percent of Subjects Achieving a Dose of CS of Less than or Equal to 7.5 mg per Day of Prednisone (or Equivalent) at Week 39

The percent of subjects whose daily CS dose prescribed at Week 39 is less or equal to 7.5 mg will be analyzed.

#### 16.3.1.4. CFB in Fasting Serum Glucose (mg/dL) at Week 39

The CFB is calculated as indicated in section 6.7.

#### 16.3.1.5. Percent of Subjects with Fasting Glucose Less than or Equal to 125 mg/dL at Week 39

The percent of subjects with fasting glucose less than or equal to 125mg/dL at Week 39 will be

Document:

CCI

Author:

PPD

Version Number:

Final 2.0

Version Date:

12Apr2019

Template No: CCI

Reference: CCI

Effective Date: 01Apr2016

Copyright © 2009, 2010, 2012, 2016 CCI. All rights reserved.

The contents of this document are confidential and proprietary to CCI. Unauthorized use, disclosure or reproduction is strictly prohibited.

calculated.

#### 16.3.1.6. Percent of Subjects Experiencing MC or Episode of MG Worsening Requiring Inpatient Care from Baseline through Week 39

Subjects who experience MC or Episode of MG worsening requiring inpatient care from baseline to Week 39 will be those who had at least one adverse event (AE) that met ALL criteria below:

- The preferred term (PT) of the AE is either “Myasthenia gravis crisis” or “Myasthenia gravis”
- The AE is serious, with the reason for seriousness being “Required/Prolonged Hospitalization”
- The onset date/time of the AE is on or after the start date/time of the first infusion of study medication, i.e., the AE is treatment-emergent
- If the subject completed the Week 39 visit, the onset date of the AE is on or prior to the date of visit for Week 39

#### 16.3.1.7. Percent of Subjects Experiencing MC or Episode of MG Worsening Requiring Inpatient Care from Week 39 to Week 45

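### No Week 39 date limit for subjects who miss that visit: after a last dose at Week 33 or 36, later hospitalisations and carried-forward values can enter secondary and exploratory Week 39 results

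*SAP*

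**What the plan says.** **Visit timing.** SAP 6.4 asks subjects who stop during treatment to return for the two follow-up visits, "Week 42 (Visit 15) and Week 45 (Visit 16) corresponding to time points 6 and 9 weeks after the last IP administration". They are reported as Early Termination 1 and 2 and are not mapped to a scheduled visit. SAP 6.5 applies no visit windows. SAP 6.4 adds: "Early termination data will be eligible for the LOCF/worst observation carried forward (WOCF; defined in Section 7.3) endpoint".

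**Carry-forward.** For continuous efficacy variables other than CS dose, SAP 7.3 states that "the last non-missing post-baseline value (including scheduled, unscheduled, and early termination) will be carried forward to impute missing values for all remaining visits". For CS dose, a separate paragraph of 7.3 uses the last eligible post-baseline value (LOCF). For discontinuations with a serious MG outcome it uses the highest eligible value, baseline included (WOCF). Both admit early termination visits, and neither gives a latest date.

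**Primary endpoint.** SAP 16.1.2 does set a limit: "The last non-missing post-baseline value (including scheduled, unscheduled, and early termination) prior to Week 39 will be carried forward".

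**Secondary percent reduction.** SAP 16.2.2.1 refers back: "the missing CS dose will be imputed using the LOCF approach for continuous endpoints as detailed in Section 7.3".

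**MG crisis or inpatient worsening, baseline through Week 39.** SAP 16.3.1.6 limits onset conditionally: "If the subject completed the Week 39 visit, the onset date of the AE is on or prior to the date of visit". The companion endpoint for Weeks 39 to 45 (SAP 16.3.1.7) takes only subjects who completed Week 39.

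**The concern.** A Week 39 endpoint should use information up to Week 39 in every subject. Here the stopping date depends on whether the subject attended the Week 39 visit, which is a post-randomisation outcome.

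The event endpoint shows this most clearly. A hospitalisation for MG at Week 43 in a subject whose last dose was Week 36 and who missed Week 39 meets every criterion in 16.3.1.6. The same event in a completer does not; it goes to 16.3.1.7.

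For scores and CS dose, an undated rule lets a programmer fill Week 39 with a value recorded 6 or 9 weeks after the last infusion, possibly after other MG treatment. The same subject could then have one Week 39 CS dose in the primary analysis and another in the secondary. If late withdrawal differs by arm, so do the measurement and at-risk times.

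**Working it through.** **1. The plan's own figures.** Protocol 5.2 gives 70% versus 30%, alpha 0.05 (two-sided, Protocol 5.1), 80% power and about 20% discontinuation.

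- n per arm = [1.960 × √(2 × 0.5 × 0.5) + 0.842 × √(0.7 × 0.3 + 0.3 × 0.7)]² / 0.40² = (1.386 + 0.546)² / 0.16 ≈ 23.3, so 24.
- Total: 48 / (1 − 0.20) = 60.
- Expected dropouts: 60 × 0.20 = 12.

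The plan's 24 and 60 are reproduced. The point does not depend on them beyond the 12.

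**2. When the follow-up visits fall** (last-dose week + 6 and + 9; 13 dosing visits, Weeks 0 to 36):

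| Last dose | Visit 1 | Visit 2 | After Week 39? |
|---|---|---|---|
| Weeks 0–27 | Weeks 6–33 | Weeks 9–36 | No |
| Week 30 | Week 36 | Week 39 | Only through the +3-day window |
| Week 33 | Week 39 | Week 42 | Visit 2 |
| Week 36 | Week 42 | Week 45 | Both |

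Only 2 of the 13 dosing visits lead to nominal visits after Week 39.

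**3. What those visits record.** Under Protocol 3.8.2.6, prescribed CS dose, QMG and MG Composite are recorded at both visits; MG-ADL and MG-QOL 15 at the second. Fasting glucose, HbA1c, IgG and AChR antibodies are scheduled at neither, so these visits do not expose them. Adverse events are collected to the last day of participation (Protocol 4.4.1).

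**4. The rules applied to a subject with last dose at Week 36 and no Week 39 visit:**

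- Primary, LOCF: values after Week 39 are excluded by 16.1.2.
- Primary, WOCF: baseline is a candidate, so the carried dose is at least the baseline dose and the reduction is at most 0%. The subject is a non-responder whatever happens later.
- Secondary percent reduction, LOCF: 16.2.2.1 leads to 7.3, with no date limit.
- Secondary percent reduction, WOCF: the maximum can be a dose from Week 42 or 45, giving a larger increase over baseline.
- Exploratory CS-dose binaries (75% reduction, CS-free, ≤7.5 mg): exposed under LOCF. Under WOCF the subject fails all three anyway (SAP 16.3.2.1).
- QMG, MG Composite, MG-ADL, MG-QOL 15: LOCF under 7.3, with no date limit.
- Inpatient MG events through Week 39: no upper onset date.

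**5. How many subjects.** Assumption, not in the documents: last doses of the 12 dropouts are spread evenly over the 13 dosing visits. Then 12 × 2/13 ≈ 1.8. The possible range is 0 to 12. One subject is 1/30 = 3.3 percentage points of a 30-subject arm, and that only if a binary status changes.

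**6. At-risk time for the event endpoint.** Follow-up to last dose + 9 weeks ends at Week 45 for a last dose at Week 36 (6/39 ≈ 15% longer than a completer) and at Week 42 for Week 33 (3/39 ≈ 8% longer). Under the same even spread the mean last dose is Week 18, so mean follow-up ends at Week 27, which is 12 weeks shorter than a completer's.

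**7. Cutoff date.** With Day 1 as the first dose (SAP 6.1), Week 39 is Day 39 × 7 + 1 = 274. Adding the 3-day visit window (Protocol 3.8.2.1) gives Day 277.

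**The case against.** The strongest reply is in SAP 7.3 itself. For all efficacy variables, a gap before the last visit is filled from the nearest earlier observation, and LOCF fills only the visits that remain. Read by calendar date, Week 39 comes before a Week 42 return, so it would be filled from Week 36 or another earlier value. This reading is sensible, and it weakens any claim that the SAP prescribes backward filling. It is only implicit, however: early termination visits have no stated position relative to Week 39. Nor does it limit the WOCF maximum or touch 16.3.1.6.

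Second, 16.3.1.6 may be deliberate. Together with 16.3.1.7 it loses no hospitalisation among discontinuers. That explains the wording, but the result no longer matches the endpoint's name, and the window still depends on completion.

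Third, other analyses are unaffected. Observed-case analyses exclude early termination data, and the four scores also have an MMRM on scheduled visits. The exposed endpoints are secondary or exploratory in a Phase 2 study without multiplicity control. All this stands and limits the importance. It does not help the inpatient-event endpoint, where the observed-case approach is the only one planned and the derivation itself lacks the limit.

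A reader might also infer that discontinuers in general are at risk for longer. Step 6 shows the opposite for most of them.

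**Conclusion.** The gap is real but narrow. For subjects without a Week 39 visit whose last dose was at Week 33 or 36, SAP 16.3.1.6 sets no upper onset date. SAP 7.3 sets no date limit for the secondary percent CS reduction, the exploratory CS-dose binaries under LOCF, QMG, MG Composite, MG-ADL and MG-QOL 15. This is inconsistent with SAP 16.1.2.

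It would be tempting to conclude that post-Week 39 data contaminate the primary result. The documents do not support that: 16.1.2 limits LOCF, and WOCF makes the subject a non-responder in any case.

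The size is about 2 subjects under the even-spread assumption, with 0 to 12 possible. That could matter for a sparse hospitalisation count and is otherwise likely to be small. Sample size and power do not change.

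**What to change.** - In SAP 7.3, define one cutoff for subjects without a Week 39 visit, for example Day 277. Allow only values dated on or before it as LOCF or WOCF candidates for Week 39, for all efficacy variables. This brings 16.2.2.1 and the exploratory endpoints into line with 16.1.2.
- In SAP 16.1.2, say that its limit means the same date, since the present wording gives none for a subject who missed the visit.
- In SAP 16.3.1.6, for these subjects, count only adverse events with onset on or before the same cutoff. List later MG hospitalisations separately, because 16.3.1.7 will not pick them up.
- Do not relabel early termination visits as Week 39 observations. That would conflict with SAP 6.4 and 6.5 and change the observed-case set.

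The cost is a few sentences before unblinding. The visit and onset dates are already used in the SAP's derivations. A few late values and events in discontinuers would leave the Week 39 analyses.
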